6.4.3.2 Eye comfort index

This questionnaire is designed to measure ocular surface irritation using Rasch analysis to produce estimates on a linear interval scale (scores: 0–100). Similar to the index for ocular surface diseases, the Ocular Comfort Index (OCI) assesses symptoms. The OCI contains six items that focus on discomfort associated with the ocular surface. Each of these questions has two parts, which separately inquire about the frequency and severity of symptoms. [44]See Appendix 14.1 Eye comfort index

The evaluator will give the questionnaire to the subject and allow them to answer it calmly without any pressure or coercion. They will only assist them if they have difficulty understanding any of the questions.

Ocular surface stains

- *Lissamine green staining* .

A drop of topical anesthetic will be instilled into the conjunctival fornix. A second drop will then be applied to the tip of the lissamine green strip and allowed to run into the fornix. It is essential to rapidly assess the staining, sequentially, first in the OD and then the OS, so that the observed patterns are equally bright. [19]See Appendix 14.2 Oxford Scale

- *Fluorescein staining*.

A drop of topical anesthetic will be instilled in the conjunctival fornix. A second drop will then be applied to the tip of the fluorescein strip and allowed to run into the fornix. It is essential to rapidly assess the staining, sequentially, first in the OD and then the OS, so that the observed patterns are equally bright. This assessment will be performed using a cobalt blue filter. [19]See Appendix 14.2 Oxford Scale

For both stains, the value obtained according to the Oxford scale will be recorded in the CRF.

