14.1 Ocular comfort index

Eye Comfort Index

Identification card	Date: / /
Study No.: SOPH172-0919-I	Subject No.: 172-_____
Subject's initials: _____	

Directions:

This questionnaire was designed to rate the comfort of your eyes.

For each question, circle your answer.

Example: In the past week, how often were your eyes red?

Never	0	1	2	3	4	5	Always	6
--------------	---	---	---	---	---	---	---------------	---

There are no right or wrong answers. Don't spend too much time on each question.

1 In the past week, how often did your eyes feel *dry* ?

Never	0	1	2	3	4	5	Always	6
--------------	---	---	---	---	---	---	---------------	---

When your eyes felt *dry*, how severe was the sensation usually?

I haven't felt it	0	1	2	3	4	5	Severe	6
--------------------------	---	---	---	---	---	---	---------------	---

2 In the past week, how often did your eyes feel *gritty* ?

Never	0	1	2	3	4	5	Always	6
--------------	---	---	---	---	---	---	---------------	---

When your eyes felt *gritty*, typically, how intense was the sensation?

I haven't felt it	0	1	2	3	4	5	Severe	6
--------------------------	---	---	---	---	---	---	---------------	---

3 In the past week, how often did your eyes feel *throbbing* ?

Never	0	1	2	3	4	5	Always	6
--------------	---	---	---	---	---	---	---------------	---

When your eyes felt like *they were stinging*, how intense was the sensation usually?

I haven't felt it	0	1	2	3	4	5	Severe	6
--------------------------	---	---	---	---	---	---	---------------	---

4 In the past week, how often did your eyes feel *tired* ?

Never	0	1	2	3	4	5	Always	6
--------------	---	---	---	---	---	---	---------------	---

When your eyes felt *tired*, how intense was the feeling usually?

I haven't felt it	0	1	2	3	4	5	Severe	6
--------------------------	---	---	---	---	---	---	---------------	---

Sheet 1 of 2

5 In the past week, how often did your eyes feel *sore* ?

Never

0 1 2 3 4 5 6 Always

When your eyes felt *sore*, how severe was the sensation usually?

I haven't felt it

0 1 2 3 4 5 6 Severe

6 In the past week, how often did your eyes feel *itchy* ?

Never

0 1 2 3 4 5 6 Always

When your eyes felt *itchy*, how intense was the sensation usually?

I haven't felt it

0 1 2 3 4 5 6 Severe

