With a statistical confidence of 95% that corresponds to type I error, equal to 1.96, with a power of 90%, corresponding to type II error, equal to 0.84.

According to the previous calculation, the result is 26 subjects, which was increased by 20% due to the probable losses. The total sample size required is **32 subjects**. So each group will be made up of 16 subjects, who will provide an eye for the analysis.

Analysis Plan [4]

Outcome Variables

Safety primary outcome variables:

- Incidence of Adverse Events.

Primary outcome variables of tolerability:

- ICO score.

Secondary Outcome Variables:

- Tear film rupture time (LRT).
- Vital signs: HR, RF and SAP.
- Posterior segment.
- Quality questionnaire.
- Intraocular pressure.
- Visual capacity.
- Laboratory Tests: BHc, QS, PFH.
- Ocular surface stains.

Table 2. Operational Definition of the Variables

Chondroitin Sulfate 0.18%/Sodium Hyaluronate 0.2%

Variable	Conceptual Definition	Operational Definition	Measurement Type	Normal value	Statistical test
Adverse events (AEs).	Any undesirable medical event that may occur in an investigational subject during the clinical research stage of a drug or vaccine but does not necessarily have a causal relationship with it. ⁴	Adverse events manifested during the conduct of the study will be collected using the CRF.	
 - Continuous quantitative. - Categorical qualitative. 	
 - Frequency: Subjects with AEs/Total number of exposed subjects. - Intensity: 0= Mild 1= Moderate 2= Severe - Causality: 0= Improbably related. 1= Probable or possibly related. 2= Related 	
 - Pearson's square chi or Fisher's exact. - U for Mann-Whitney.
Changes in Intraocular Pressure (IOP).	Tonometry is the objective measurement of IOP, based primarily on the force required to flatten the cornea or the degree of corneal indentation produced by a fixed force.	Goldmann tonometry. 3 samples will be taken, which will be recorded in the clinical file and the average will be recorded in the CRF.	
 - Continuous quantitative. 	
 - 11-21 mmHg. 	
 - U for Mann-Whitney. - Wilcoxon Ranges.

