Eye Comfort Index (ICO) score.	The ICO is a questionnaire designed to measure irritation of the ocular surface, it assesses symptoms	The evaluator will apply the questionnaire to the subject and allow the subject to answer it calmly without any pressure and/or	Discrete quantitative.	
 Score: 0= None, 100 = High discomfort. 	
 - U for Mann-Whitney. - Wilcoxon Ranges.

Chondroitin Sulfate 0.18%/Sodium Hyaluronate 0.2%

	focused on the comfort associated with ocular surface alterations. Elevated values indicate more Severe.	coercion. See ICO Annex.			
Changes in visual capacity (CV)	Visual acuity (VA) is a test of visual function. Spatial VA is the ability to distinguish separate elements of an object and identify them as a whole. It is quantified as the minimum angle of separation (located at the nodal point of the eye) between two objects that allows them to be perceived as separate objects.	Snellen's Primer	Discrete quantitative.	Fraction, normal value = 20/20	
 - U for Mann-Whitney. - Wilcoxon Ranges.
Changes in tear film rupture time (LRT) with fluorescein.	The stability of the tear film is usually evaluated in the clinic by the TRL. It consists of instilling fluorescein on the ocular surface to allow the visualization of the tear film	It will be measured at the end of a blink and will be asked not to blink immediately until the tear film on the cornea is broken.	Continuous quantitative.	> 10 seconds.	
 - U for Mann-Whitney. - Wilcoxon Ranges.

Chondroitin Sulfate 0.18%/Sodium Hyaluronate 0.2%

	and measure the time it takes to break since the last blink.				
Changes in corneal and conjunctival staining with lysmine green.	Detection of epithelial defects in the conjunctiva and cornea.	Direct observation with slit lamp, Oxford scale graduation. See annex Oxford scale.	Ordinal Qualitative	
Degrees:
 
The staining is presented by a series of panels (A-E). Stain points range from 0-5 for each panel and 0-15 for the total exposed area of the conjunctiva and cornea.
	
 - Pearson's square chi or Fisher's exact. - McNemar test (if applicable).

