
 
 I haven't felt it	0	1	2	3	4	5	Severe	
 
 							6	
 
							I haven't felt it	0	1	2	3	4	5	Severe								6
I haven't felt it	0	1	2	3	4	5	Severe															
							6															
2 In the past week, how often did your eyes feel gritty ?																						

 
 Never	0	1	2	3	4	5	Always	
 
 							6	
 
							Never	0	1	2	3	4	5	Always								6
Never	0	1	2	3	4	5	Always															
							6															
When your eyes felt gritty, typically, how intense was the sensation?																						

 
 I haven't felt it	0	1	2	3	4	5	Severe	
 
 							6	
 
							I haven't felt it	0	1	2	3	4	5	Severe								6
I haven't felt it	0	1	2	3	4	5	Severe															
							6															
3 In the past week, how often did your eyes feel throbbing ?																						

 
 Never	0	1	2	3	4	5	Always	
 
 							6	
 
							Never	0	1	2	3	4	5	Always								6
Never	0	1	2	3	4	5	Always															
							6															
When your eyes felt like they were stinging , how intense was the sensation usually?																						

 
 I haven't felt it	0	1	2	3	4	5	Severe	
 
 							6	
 
							I haven't felt it	0	1	2	3	4	5	Severe								6
I haven't felt it	0	1	2	3	4	5	Severe															
							6															
4 In the past week, how often did your eyes feel tired ?																						

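### As printed, item 3 of the eye comfort index asks how often the eyes throb but how intensely they sting, and the form carries another study's code

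*Protocol*

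**What the plan says.** Protocol section 6.4.1.1 lists the eye comfort index as the only primary tolerability variable. The SAP does the same under "Primary outcome variables of tolerability". Protocol section 6.4.3.2 describes six items about ocular surface discomfort and adds: "Each of these questions has two parts, which separately inquire about the frequency and severity of symptoms". The same section says that Rasch analysis yields scores from 0 to 100, and SAP Table 2 gives the range as "0= None, 100 = High discomfort".

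The form is reproduced in protocol section 14.1 and in the SAP annex. The frequency part of item 3 in the protocol reads "In the past week, how often did your eyes feel *throbbing". The intensity part reads "When your eyes felt like *they were stinging*, how intense was the sensation usually". The SAP annex has "how often did your eyes feel throbbing" for frequency and again *stinging* for intensity.

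The protocol form is headed "Study No.: SOPH172-0919-I", with a subject number that starts with 172. The SAP annex has the same header. Section 6.2.4 builds the subject number from the three digits of the molecule, then the centre and the sequence number. Section 8.2 treats this questionnaire as source data and bars site staff from altering what a subject wrote on it.

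**The concern.** A two-part item is interpretable only if both parts concern one symptom. As item 3 is printed, a subject whose eyes sting but do not throb has to circle *Never* and then rate an intensity. The form has no place to record how often the stinging occurred.

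The decision rule is what makes this matter. Protocol section 8.3.1 and the SAP call the product safe and tolerable when the primary variables show no clinical or statistical difference from the comparator. A faulty item is the same in both arms, so it does not by itself favour either one. It does add noise, which tends to hide a difference, and under this rule a hidden difference counts in the product's favour. The groups have 16 subjects each.

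The header points to a form carried over from another study without being re-identified. That is a reason to check the item wording as well.

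**Working it through.** **The plan's own figure.** The 0–100 range cannot be reproduced. The protocol attributes it to Rasch analysis, and neither document gives a conversion table or item parameters.

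**Item wording.** The symptom words are the same in protocol section 14.1 and the SAP annex:

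| Item | Frequency part | Intensity part | Same symptom? |
|---|---|---|---|
| 1 | dry | dry | yes |
| 2 | gritty | gritty | yes |
| 3 | throbbing | stinging | **no** |
| 4 | tired | tired | yes |
| 5 | sore | sore | yes |
| 6 | itchy | itchy | yes |

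Five of the six items show the intended structure, and item 3 departs from it.

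**Share of the form.** There are 6 items × 2 parts = 12 answers. Item 3 supplies 2/12 = 16.7% of them, and its frequency part supplies 1/12 = 8.3%. In printed response points, each answer running from 0 to 6, the shares are 12/72 and 6/72, which are the same percentages. They describe the form's content. They are not weights in the Rasch score, which the documents do not give.

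**What the printed item records**, if subjects see the same wording:

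- Stinging without throbbing: frequency 0, intensity above 0. The pair is contradictory.
- Throbbing without stinging: frequency above 0, intensity 0. This is also contradictory.
- Both: two non-zero answers about different symptoms.
- Neither: 0 and 0, with no harm done.

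At one extreme, constant severe stinging without throbbing gives 0 + 6 = 6 points, where an item worded for stinging throughout would give 6 + 6 = 12. The error can also go upwards: a subject who throbs often and stings rarely gets a frequency answer too high for stinging. The direction depends on the subject, so no net bias can be computed from the documents.

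**Header.**

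| | This trial | Printed form |
|---|---|---|
| Study code | SOPH165-0217/I | SOPH172-0919-I |
| Subject prefix | 165 (section 6.2.4) | 172 |

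The schedule in section 6.5 has the index at the baseline and final visits. With 32 subjects that is up to 32 × 2 = 64 forms.

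**Sample size.** The calculated 26, raised to 32, rests on a formula for proportions and does not use the index, so it is unaffected.

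**The case against.** The strongest reply is that item 3 is a translation artefact. The protocol summary gives the study title in Spanish, and the English shows literal renderings elsewhere: a column for variable type is headed *Guy*, and the preservative in the formulation table is called *Conservative*. *Throbbing* and *stinging* may both stand for one Spanish word. The SAP annex is no independent confirmation, since it repeats both the wording and the wrong header and looks like a copy. Section 6.4.3.2 also does not say in so many words that both parts must concern the same symptom. That is an inference, though the other five items support it.

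This reply stands as far as it goes. The Spanish form is not in the documents, so harm to the data is conditional. It does not remove the need to check, and it does not explain the header.

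A reader might infer three stronger points that the documents do not support:

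- *That the form yields 0–72 while the SAP analyses 0–100.* The sum of 72 arises only if the answers are simply added, which neither document prescribes. Section 6.4.3.2 names a Rasch score of 0–100. Only the conversion reference is missing. The SAP's between-group Mann-Whitney test would be unchanged by any order-preserving conversion of the total.
- *That the forms cannot be attributed to this trial's subjects.* Initials, the date and the rest of the subject number are still recorded, and monitors compare source documents with the case report form. The header is a correctable template error.
- *That item 3 is the item closest to instillation irritation.* Section 5.5.3 names burning, foreign body sensation and itching as the tolerability symptoms, and the gritty and itchy items are printed consistently. Post-instillation symptoms are also reviewed from the diary (section 6.5.1.3), and adverse events are recorded separately.

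**Conclusion.** The printed form is wrong in two places, and both annexes carry both errors. Item 3 names two different symptoms, and the header belongs to another study.

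For item 3 the consequence depends on one assumption, that the Spanish form has the same mismatch. If it does, one item of six (2 of 12 answers, 16.7%) in the sole primary tolerability variable does not describe a single symptom, and the frequency of stinging goes unrecorded. The effect on the 0–100 score cannot be sized without the Rasch conversion. If the Spanish form uses one word, the fault is confined to the English annexes. It would go too far to say that the trial under-records stinging: the subject's form has not been seen, and stinging can also surface in the diary or as an adverse event.

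The wrong study code and prefix are certain but change no result. Overall this should be fixed, and for item 3 that is conditional on the Spanish form.

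**What to change.** 1. Compare item 3 with the validated Spanish version of the index, and use the same symptom word in both parts of the subject form, protocol section 14.1 and the SAP annex.
2. Reissue the form with study code SOPH165-0217/I and subject prefix 165-.
3. Do both before the first baseline form is completed. Section 8.2 does not let site staff alter a subject's answers, so a mismatched item cannot be repaired afterwards.
4. As a documentation note only, add a sentence to the SAP citing the instrument's own Rasch conversion to the 0–100 score.

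The cost is a reprinted two-page form, two corrected annexes, one SAP sentence and notification of the committees about a corrected subject document. Sample size, visits and the choice of tests do not change.

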14.2 Oxford Scale

PANEL	Grade	Criteria
A	0	Equal to or less than panel A
B	I	Equal to or less than panel B, greater than panel A
C	II	Equal to or less than panel C, greater than panel B
D	III	Equal to or less than panel D, greater than C
E	IV	Equal to or less than panel E, greater than panel D
>E	V	Greater than panel E

Excelencia en oftálmicos

Statistical Analysis Plan

Phase I clinical study, to evaluate the safety and tolerability of PRO-165 ophthalmic gel versus Artelac® Nighttime Gel, on the ocular surface of ophthalmologically and clinically healthy subjects.

Date of creation: July 2017.

Phase I clinical study, to evaluate the safety and tolerability of PRO-165 ophthalmic gel versus Artelac® Nightime Gel, on the ocular surface of ophthalmologically and clinically healthy subjects.

Protocol Code: SOPH165-0217/I.

Protocol Version: 2.0

Content

1.0	Abbreviations.....	3
2.0	Objectives of the Study.....	3
3.0	Study Design SOPH165-0217/I.....	4
4.0	Sample Size.....	5
5.0	Sample Size Calculation.....	6
7.0	Methods of Analysis.....	11
8.0	Changes.....	15
9.0	References.....	13
10.0	Annexes.....	16

Abbreviations

BHc	Complete hematic biometry
CRF	Electronic Case Report Form
VA	Visual Ability
AE	Adverse events
HR	Heart rate
FCI	Informed Consent Form
FR	Respiratory rate
HC	Conjunctival hyperemia
ICO	Eye Comfort Index
ITT	Population by intent to treat
SC	Safety call
MC	Concomitant medication
PFH	Liver function tests
RP	Research Product
IOP	Intraocular pressure
PP	Population by protocol
PRO-165	Chondroitin sulfate 0.18%/Sodium hyaluronate 0.2%
BC	Blood chemistry
SBP	Systemic blood pressure
TBUT	Tear break-up time
BV	Initial visit
FV	Final visit

Objective of the Study

To evaluate the safety and tolerability of the PRO-165 formulation on the ocular surface of ophthalmologically and clinically healthy subjects.

Study Hypothesis

H0: PRO-165 Ophthalmic Gel has a similar safety and tolerability profile to Artelac® Nighttime Gel in ophthalmologically and clinically healthy subjects.

H1: PRO-165 Ophthalmic Gel has a different safety and tolerability profile than Artelac® Nighttime Gel in ophthalmologically and clinically healthy subjects.

Study Design SOPH165-0217/I

Phase I, controlled, parallel-group, double-blind, randomized, exploratory clinical trial.

Duration of treatment

Treatment: 10 days.

Study period: 4 months.

Table 1. Study timeline

Procedures	Scrutiny	Basal Visit	Visit 1	Final Visit	Call Security
	Day 0 - X ^{to}	Day 0	Day 5 ± 2	Day 11 to + 1	Day 13 ± 1
CI Signature	X				
Medical history	X				
Ophthalmological medical history	X				
Laboratory sample collection	X			X	
Review of Laboratory Tests		X			X
Pregnancy Test	X			X	
Eligibility Criteria	X	Xb			
Allocation		X			

Chondroitin Sulfate 0.18%/Sodium Hyaluronate 0.2%

Delivery of intervention	Xc			
Return of intervention	X			
Adherence assessment		X	X	
Adverse events		X	X	X
Intraocular pressure	X	1 x	X	X
Visual Ability	X	1 x	X	X
TRL	X	1 x	X	X
Ocular surface stains	X	1 x	X	X
Vitals	X	1 x	X	X
Eye Comfort Index		X		X
Subject Diary Delivery		X	X	
Return / Evaluation of the subject's Journal			X	X
Return and Evaluation of the Quality Questionnaire				X
Subject continuity assessment			X	

^a The counting visit may be up to 10 days prior to the baseline, if it exceeds these the subject will not be able to enter.

^b These criteria shall be supplemented by the results of laboratory examinations and those collected during the screening visit.

^c An indication will be given to start the application the next day.

¹ They can be taken from the scrutiny visit, as long as no more than 10 days have elapsed, it is the prerogative of the PI to measure them again at the baseline visit.

Sample Size

An estimated 32 evaluable subjects are divided, divided into two groups [16 subjects (16 eyes) exposed per group].

[figure not shown]

Figure 1. Suggested work scheme.

Sample Size Calculation

There are no references to sample size calculation in phase I studies, and the formulation of Humylub Ofteno® has not reported adverse events in its periodic safety reports. For this reason, it was considered pertinent to base it on the calculations of previous phase I studies, carried out by Laboratorios Sophia, S.A. de C.V., with formulations of ocular lubricants in the same pharmaceutical presentation.

The calculation was in accordance with the presentation of adverse events reported by Christ T (1994), in a randomized, single-blind, parallel-group controlled clinical trial where the efficacy and tolerance of a 5% dexpanthenol ophthalmic gel versus a 5% panthenol ointment in 48 subjects with corneal erosion was evaluated. keratoconjunctivitis from UV radiation or similar conditions. The intervention consisted of the application of 1 cm of the gel and ointment for 4 and 3 days, respectively. [1][2]

The percentage of good tolerance that was presented with the gel was 25%, so it is expected that no more than 10% of the subjects report a bad tolerance with the formulation proposed in this protocol.

The sample size was calculated using the formula for proportions.[3]

$$n = p(1 - p) \left(\frac{z_{1-\alpha} + z_{1-\beta}}{p - p_0 - \delta} \right)^2$$

With a statistical confidence of 95% that corresponds to type I error, equal to 1.96, with a power of 90%, corresponding to type II error, equal to 0.84.

According to the previous calculation, the result is 26 subjects, which was increased by 20% due to the probable losses. The total sample size required is **32 subjects**. So each group will be made up of 16 subjects, who will provide an eye for the analysis.

Analysis Plan [4]

Outcome Variables

Safety primary outcome variables:

- Incidence of Adverse Events.

Primary outcome variables of tolerability:

- ICO score.

Secondary Outcome Variables:

- Tear film rupture time (LRT).
- Vital signs: HR, RF and SAP.
- Posterior segment.
- Quality questionnaire.
- Intraocular pressure.
- Visual capacity.
- Laboratory Tests: BHc, QS, PFH.
- Ocular surface stains.

Table 2. Operational Definition of the Variables

Chondroitin Sulfate 0.18%/Sodium Hyaluronate 0.2%

Variable	Conceptual Definition	Operational Definition	Measurement Type	Normal value	Statistical test
Adverse events (AEs).	Any undesirable medical event that may occur in an investigational subject during the clinical research stage of a drug or vaccine but does not necessarily have a causal relationship with it. ⁴	Adverse events manifested during the conduct of the study will be collected using the CRF.	
 - Continuous quantitative. - Categorical qualitative. 	
 - Frequency: Subjects with AEs/Total number of exposed subjects. - Intensity: 0= Mild 1= Moderate 2= Severe - Causality: 0= Improbably related. 1= Probable or possibly related. 2= Related 	
 - Pearson's square chi or Fisher's exact. - U for Mann-Whitney.
Changes in Intraocular Pressure (IOP).	Tonometry is the objective measurement of IOP, based primarily on the force required to flatten the cornea or the degree of corneal indentation produced by a fixed force.	Goldmann tonometry. 3 samples will be taken, which will be recorded in the clinical file and the average will be recorded in the CRF.	
 - Continuous quantitative. 	
 - 11-21 mmHg. 	
 - U for Mann-Whitney. - Wilcoxon Ranges.
Eye Comfort Index (ICO) score.	The ICO is a questionnaire designed to measure irritation of the ocular surface, it assesses symptoms	The evaluator will apply the questionnaire to the subject and allow the subject to answer it calmly without any pressure and/or	Discrete quantitative.	
 Score: 0= None, 100 = High discomfort. 	
 - U for Mann-Whitney. - Wilcoxon Ranges.

Chondroitin Sulfate 0.18%/Sodium Hyaluronate 0.2%

	focused on the comfort associated with ocular surface alterations. Elevated values indicate more Severe.	coercion. See ICO Annex.			
Changes in visual capacity (CV)	Visual acuity (VA) is a test of visual function. Spatial VA is the ability to distinguish separate elements of an object and identify them as a whole. It is quantified as the minimum angle of separation (located at the nodal point of the eye) between two objects that allows them to be perceived as separate objects.	Snellen's Primer	Discrete quantitative.	Fraction, normal value = 20/20	
 - U for Mann-Whitney. - Wilcoxon Ranges.
Changes in tear film rupture time (LRT) with fluorescein.	The stability of the tear film is usually evaluated in the clinic by the TRL. It consists of instilling fluorescein on the ocular surface to allow the visualization of the tear film	It will be measured at the end of a blink and will be asked not to blink immediately until the tear film on the cornea is broken.	Continuous quantitative.	> 10 seconds.	
 - U for Mann-Whitney. - Wilcoxon Ranges.

Chondroitin Sulfate 0.18%/Sodium Hyaluronate 0.2%

	and measure the time it takes to break since the last blink.				
Changes in corneal and conjunctival staining with lysmine green.	Detection of epithelial defects in the conjunctiva and cornea.	Direct observation with slit lamp, Oxford scale graduation. See annex Oxford scale.	Ordinal Qualitative	
Degrees:
 
The staining is presented by a series of panels (A-E). Stain points range from 0-5 for each panel and 0-15 for the total exposed area of the conjunctiva and cornea.
	
 - Pearson's square chi or Fisher's exact. - McNemar test (if applicable).
Corneal and conjunctival staining changes with fluorescein.	Detection of epithelial defects in the conjunctiva and cornea.	Direct observation with slit lamp and cobalt blue filter, Oxford scale graduation. See annex Oxford scale.	Ordinal Qualitative	
Degrees:
 
The staining is presented by a series of panels (A-E). Stain points range from 0-5 for each panel and 0-15 for the total exposed area of the conjunctiva and cornea.
	
 - Pearson's square chi or Fisher's exact. - McNemar test (if applicable).
Incidence of alterations in laboratory test results.	The normal parameters to be considered will be the ranges established by the laboratory, with a lower and upper margin of 20% in a clinically healthy subject, according to the PI's criteria.	Laboratory analysis.	Continuous quantitative.	
See annex Scales to be used for vital signs and laboratory analysis.
	
 - U for Mann-Whitney. - Wilcoxon Ranges.

Chondroitin Sulfate 0.18%/Sodium Hyaluronate 0.2%

Incidence of alterations in HR.	The normal parameters to be considered will be the ranges established by the laboratory, with a lower and upper margin of 20% in a clinically healthy subject, according to the PI's criteria.	Auscultation with a stethoscope.	Continuous quantitative.	60-100 lpm.	- U for Mann-Whitney. - Wilcoxon Ranges.
Incidence of alterations in RF.	The normal parameters to be considered will be the ranges established by the laboratory, with a lower and upper margin of 20% in a clinically healthy subject, according to the PI's criteria.	Auscultation with a stethoscope.	Continuous quantitative.	12-24 rpm.	- U for Mann-Whitney. - Wilcoxon Ranges.
Incidence of abnormalities in SBP.	The normal parameters to be considered will be the ranges established by the laboratory, with a lower and upper margin of 20% in a clinically healthy subject, according to the PI's criteria.	Measurement with sphygmomanometer.	Continuous quantitative.	< 120 / 80 mmHg	- U for Mann-Whitney. - Wilcoxon Ranges.

Methods of Analysis [4]

Chondroitin Sulfate 0.18%/Sodium Hyaluronate 0.2%

The statistical analysis will be carried out by personnel of Laboratorios Sophia, S.A. de C.V. The statistical program SPSS version 19.0 (IBM Corporation, Armonk, NY, USA) will be used. Designated personnel will be blinded to intervention groups. Coding will be performed using consecutive numbers for each intervention group.

The data will be collected and sorted in an Excel spreadsheet (Microsoft® Office). The data will then be exported to the SPSS program platform. The variables will be categorized according to their nature (see [Table 2](#)).

Study participants will be identified by a number and their initials.

The initials of the study subject will be obtained starting with the first letter of the name, followed by the first letter of the first surname and the first letter of the second surname, obtaining a maximum of three letters, in case the person has two names or compound surname, the first letter will always be used.

Example:

To. [name]	B. [name]
to. Initials: AMC	b. Initials: JDO

Once the subject has been selected, they will be assigned a number with which they will be identified throughout the study. This code will be made up of eight numbers in the following order from left to right:

- Three digits of the molecule under study according to the name by the sponsor.
- Two digits corresponding to the research centre number.
- Three digits of the number following their inclusion assigned to the research centre.

The results of the continuous quantitative variables will be presented in measures of central tendency: mean, standard deviation and ranges, see [Table 2](#).

The Kolmogorov-Smirnov and Shapiro Wilk test will be performed to determine the type of distribution of the data (normality) in the results obtained in each study group. [5]

The statistical analysis of the continuous quantitative variables to find significant differences (p) will be as follows:

- Intra-group analysis: will be determined by Wilcoxon's rank test, for quantitative variables. [6]
- Inter-group analysis: Differences between groups will be analyzed using the Mann-Whitney U statistic.

The level of difference to consider significance will be an alpha (α) of 0.05 or less. A 95% CI will be considered for the non-inferiority criteria.

The result of the nominal and ordinal qualitative variables will be presented in frequencies, proportions and percentages, see [Table 2](#).

The statistical analysis to identify significant differences in the qualitative variables will be carried out by creating 2x2 contingency tables and will be carried out as follows:

- Intra-group difference: McNemar test. This is applied to 2x2 contingency tables with a dichotomous feature, with pairs of paired subjects, to determine if the marginal frequencies of row and column are equal (marginal homogeneity).
- Difference between groups: Pearson's Chi-square (χ^2) test or Fisher's exact test at expected values less than 5.

The level of difference to consider significance (p) will be an alpha (α) of 0.05 or less.

Chondroitin Sulfate 0.18%/Sodium Hyaluronate 0.2%

For the reporting of adverse events, all eyes of those participants who were randomly assigned to an intervention group after PI instillation (ITT) will be considered.

The final report of the results will be shown in tables or graphs, as appropriate.

Those subjects who meet a minimum adherence of 60% will be included in the statistical analysis to meet the objective of the study, taken from the subject's diary. However, even if the subject's adherence is greater than 60% per diary, if the adherence calculated by weight is less than 30%, the subject will not be included.

The investigational drug will be considered safe and tolerable when there are no clinical and statistical differences in all primary outcome variables, with respect to its comparator (Artelac® Nighttime Gel).

Table 3. Triangulation of concepts

Variable Type	Variable	A1	B1	B2	C1	D1	E1	E2	E3	E4	E5	E6	E7	E8
Background														
A1	Demographic			DT										
Basal														
B1	Medical History		DT			T								
B2	Comprehensive ophthalmological evaluation		DT	DT		TB			TB		B	B		T
Safety														
C1	Incidence of AD			TB	TB		TB	TB	TB		TB	TB	TB	TB
Tolerability														
D1	ICO			DB			DB							
Secondary outcome														
E1	TRL			DB		TB		DB						
E2	Vitals			DB		TB			B					

Chondroitin Sulfate 0.18%/Sodium Hyaluronate 0.2%

E3	Posterior segment	DB	TB	B
E4	Quality Questionnaire			TB
E5	PIO	DB	TB	B
E6	Visual Ability	DB	TB	B
E7	Laboratory tests	DB	TB	B
E8	Ocular surface stains	TB	TB	TB

D. Descriptive Statistics; T, 2x2 contingency table; B, Bivariate Analysis; M, Multivariate Analysis.

Changes

1. First version of the document, no changes apply.

Author of the document

Ph.D. in Cs. [name].

Biostatistics.

Clinical Operations.

Laboratorios Sophia, S.A. de C.V.

[name]

[name]

References

<https://doi.org/10.1007/BF03163747>.
